8.1.2 Tumor Imaging During the Study

Tumor imaging should be continued on study treatment and the same imaging technique should be used in a subject throughout the study. Imaging should be performed every 9 weeks (± 7 days) from the first dose of study treatment or more frequently if clinically indicated. Imaging should not be delayed for delays in cycle starts or extension of combination treatment cycle intervals.

Imaging should continue to be performed until documented PD, the start of new anticancer treatment, withdrawal of consent, death, or the end of the study, whichever occurs first. PD should be confirmed at least 4 weeks after the first scan indicating PD in clinically stable subjects.

Table 12 Imaging and Treatment After First Radiologic Evidence of Progressive Disease

	Clinically Stable		Clinically Unstable	
	Imaging	Treatment	Imaging	Treatment
First radiologic evidence of PD	Repeat imaging at ≥ 4 weeks to confirm PD	Should continue study treatment while awaiting confirmatory scan	Repeat imaging at ≥ 4 weeks to confirm PD if possible	Discontinue treatment
Repeat scan confirms PD	No additional imaging required	Discontinue treatment	No additional imaging required	N/A
Repeat scan shows SD*, PR*, or CR*	Continue regularly scheduled imaging assessments every 9 weeks	Continue study treatment	Continue regularly scheduled imaging assessments every 9 weeks	May restart study treatment if condition has improved and/or clinically stable per investigator's discretion**
* SD, PR, CR is based on new baseline from first evidence of PD				
**If treatment is delayed contact the Medical Monitor to review treatment plans (Section 5.4.1)				

In determining whether or not the tumor burden has increased or decreased, site study team should consider all target lesions as well as non-target lesions.

Scenarios where PD is confirmed at repeat imaging:

- Tumor burden remains $\geq 20\%$ and at least 5 mm absolute increase compared to prior scan
- Non-target disease resulting in initial PD is worse (qualitative)
- New lesion resulting in initial PD is worse (qualitative)
- Additional new lesion(s) since last evaluation

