10.2.1.2 Progression-Free Survival

PFS is defined as the time from the date of first dose to PD or death due to any cause. Subjects who do not experience PD and do not die on or before the data cut-off date will be censored at the time of last tumor assessment or data cut-off date, whichever is earlier. Subjects who do not experience PD and start new systemic therapy will be censored at the time the new systemic therapy was begun or the data cut-off date, whichever is earlier. Subjects with no assessments of PD will be censored at the time of first dose. Subjects who are lost to follow up for assessment of PD will be censored at their last tumor assessment or data cut-off date whichever is earlier. Kaplan-Meier methodology will be used to estimate median PFS for each cohort in Phase 1 and in each Arm in Phase 2.

The primary definition of PD for PFS is based on mRECIST. Analyses will be performed separately using objective disease responses definitions based on the mRECIST, RECIST v1.1, and GCIG CA-125 criteria. Analysis repeated for RECIST v1.1 and GCIG CA-125 are considered supportive.

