10.2.4 Sample Size Determination

During Phase 1, dose escalation will be based on traditional escalation guidelines (3+3) to determine the RP2D and evaluate safety data (including DLTs and adverse events) of each planned treatment.

Phase 2 will be an open-label, randomized study design conducted in 2 stages to achieve up to 27 treated subjects per Arm. After 13 subjects in an Arm are randomized at the confirmed dose following the Safety Run-in (stage 1), an additional 14 subjects will be enrolled in that Arm (stage 2) if 1 or more subjects respond or if the median PFS is at least 4.8 months. If the criteria for either ORR or PFS are not met, the preliminary anti-tumor activity in the Arm will be rejected and no further subjects will be randomized to the Arm. If the Arm goes on to stage 2, a total of 27 treated subjects will be studied in that Arm. The Arm will be considered successful if 4 or more subjects respond or the median PFS is at least 4.8 months. If the criteria for either ORR or PFS are not met, the Arm will be rejected. This design is applied to each Arm independently. There are no formal comparisons planned between Arms.

This is an exploratory study of each Arm where the sample size and ORR and PFS criteria for each stage are based on clinical judgement; each Arm is assumed to be evaluated separately. Type I error will not be controlled over both Arms. The ORR criteria and number of subjects for each stage within Arm are based on a Simon minimax 2-stage design (null hypothesis that $ORR \leq 0.05$ versus the alternative that $ORR \geq 0.20$ with $\alpha = 0.05$ and $\text{power} = 0.80$). The PFS criteria are based on the lower limit of the 95% CI determined based on meta-analysis in the 3rd relapse patient population where the median PFS is 5.6 months, (95% CI: 4.8 to 6.2 months).⁶⁷ The one-sided test for PFS (i.e. observing median $PFS \geq 4.8$ months) has a Type I error rate of 0.0744 when the null hypothesis is that the median $PFS = 3.6$ months, PFS is exponentially distributed, accrual is uniform, and total study duration is 30 months for 27 subjects enrolled over 24 months. For a one-sided test of observing $PFS \geq 4.8$ months, there is approximately 77% power to detect a median PFS of 5.6 months and 50% power to detect a median PFS of 4.8 months.

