Assuming a non-negative correlation between the one-sided tests for ORR and PFS, the overall Type I error for either test criteria being met is at most 0.1203. There is at least 70% power to meet at least one of the test criteria if $ORR = 0.25$ and median $PFS = 4.8$ and at least 79% power if $ORR = 0.25$ and median $PFS = 5.6$.

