3.3. Sample Size Considerations

During Phase 1, dose escalation will be based on traditional escalation guidelines (3+3) to determine the RP2D and evaluate safety data (including DLTs and adverse events) of each planned treatment.

Phase 2 will be an open-label, randomized study design conducted in 2 stages to achieve up to 27 treated subjects per Arm. After 13 subjects in an Arm are randomized at the confirmed dose following the Safety Run-in (Stage 1), an additional 14 subjects will be enrolled in that Arm (Stage 2) if 1 or more subjects respond or if the median PFS is at least 4.8 months. If the criteria for either ORR or PFS are not met, the preliminary anti-tumor activity in the Arm will be rejected and no further subjects will be randomized to the Arm. If the Arm goes on to stage 2, a total of 27 treated subjects will be studied in that Arm. The Arm will be considered successful if 4 or more subjects respond or the median PFS is at least 4.8 months. If the criteria for either ORR or PFS are not met, the Arm will be rejected. This design is applied to each Arm independently. There are no formal comparisons planned between Arms.

This is an exploratory study of each Arm where the sample size and ORR and PFS criteria for each stage are based on clinical judgement; each Arm is assumed to be evaluated separately. Type 1 error will not be controlled over both Arms. The ORR criteria and number of subjects for each stage within Arm are based on a Simon minimax 2-stage design (null hypothesis that $ORR \leq 0.05$ versus the alternative that $ORR \geq 0.20$ with $\alpha = 0.05$ and $\text{power} = 0.80$). The PFS criteria are based on the lower limit of the 95% CI determined based on meta-analysis in the 3rd

Sponsor: Aduro Biotech, Inc.
Protocol Number: ADU-CL-11
Version and Date: Version 1.0, 03MAY2018

relapse patient population where the median PFS is 5.6 months, (95% CI: 4.8 to 6.2 months) (Hanker, 2012). The one-sided test for PFS (i.e. observing median PFS \geq 4.8 months) has a Type I error rate of 0.0744 when the null hypothesis is that the median PFS=3.6 months, PFS is exponentially distributed, accrual is uniform, and total study duration is 30 months for 27 subjects enrolled over 24 months. For a one-sided test of observing PFS \geq 4.8 months, there is approximately 77% power to detect a median PFS of 5.6 months and 50% power to detect a median PFS of 4.8 months.

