Assuming a non-negative correlation between the one-sided tests for ORR and PFS, the overall Type I error for either test criteria being met is at most 0.1203. There is at least 70% power to meet at least one of the test criteria if ORR=0.25 and median PFS=4.8 and at least 79% power if ORR=0.25 and median PFS=5.6.

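### The stated error and power of the PFS rule belong to an exponential-model median, not to the Kaplan-Meier median that the protocol specifies; for the Kaplan-Meier rule the overall bound of 0.1203 does not hold

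*Protocol*

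**What the plan says.** Protocol 10.2.4 calls an arm successful if at least 4 of 27 subjects respond or if median PFS is at least 4.8 months. It says that the PFS test "has a Type I error rate of 0.0744 when the null hypothesis is that the median" PFS is 3.6 months. SAP 3.3 repeats the rule and says that the PFS test "has a Type I error rate of 0.0744 when the null hypothesis is that the median PFS=3.6 months". Both documents assume exponential PFS and, in the protocol's words, "accrual is uniform, and total study duration is 30 months for 27 subjects enrolled over 24 months". Both give power of about 77% at a median of 5.6 months and 50% at 4.8 months. For the two criteria together, assuming non-negative correlation, Protocol 10.2.4 states that "the overall Type I error for either test criteria being met is at most 0.1203".

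On estimation, Protocol 10.2.1.2 says "Kaplan-Meier methodology will be used to estimate median PFS for each cohort in Phase 1 and in each Arm in Phase 2". SAP 7.1 derives individual PFS times but names no estimator of the median. On timing, Protocol 8.1.2 says "Imaging should be performed every 9 weeks", with a 7-day window either side and more often if clinically indicated. SAP 7 dates confirmed progression to the scan that first showed it.

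**The concern.** An error rate describes a particular decision rule, and the rule here is a threshold on a Kaplan-Meier median. With 27 subjects that median depends on a single order statistic and is much noisier than an exponential-model estimate, which uses all events and all follow-up time. A figure derived for the second understates the false-positive risk of the first. Dating progression to scans adds a further problem, because the 4.8-month bar lies between two scheduled scans. At stake is how an arm that clears the bar is read: the stated 0.0744 and the ceiling of 0.1203 suggest more protection against calling an inactive arm successful than the rule gives.

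**Working it through.** **Inputs.** From Protocol 10.2.4: exponential PFS, null median 3.6 months, n = 27, uniform accrual over 24 months, 30 months in total (so at least 6 months of follow-up), bar 4.8 months, and a Simon minimax design for ORR with null 0.05. The success limit is 4 of 27, and stage 1 continues on at least 1 response in 13 or a median PFS of at least 4.8 months. From SAP 5.3: 30.4375 days per month.

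**Step 1: reproduce the plan's figures.** With L = ln 2 / m, the expected number of events is d = 27 × [1 − (exp(−6L) − exp(−30L)) / (24L)]. For an exponential-model estimate, the log median is approximately normal with variance 1/d.
- m = 3.6: d = 25.18; 1 − Φ(ln(4.8/3.6) × √25.18) = 0.0744.
- m = 5.6: d = 22.90; Φ(ln(5.6/4.8) × √22.90) = 0.770.
- m = 4.8: 0.500.

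All three match. The overall 0.1203 is close to 1 − (1 − 0.0744)(1 − 0.05) = 0.1207, but does not reproduce exactly. With the Simon design's actual error of 0.0416 the same formula gives 0.113.

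**Step 2: the Kaplan-Meier rule, exact event times.** Nobody is administratively censored before 6 months. The Kaplan-Meier median of 27 subjects is the 14th event time, so it is at least 4.8 months when at least 14 of 27 are event-free at 4.8 months.
- m = 3.6: S(4.8) = 0.5^(4.8/3.6) = 0.397; P(Bin(27, 0.397) ≥ 14) = 0.137.
- m = 5.6: 0.708. m = 4.8: 0.500.

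**Step 3: overall error, exact times.** With ORR independent of PFS and no stage 1 rule, 1 − (1 − 0.137)(1 − 0.0416) = 0.173. Simulation of 20,000 trials with the stage 1 rule applied, and at least 6 months of follow-up on the first 13 subjects, gives 0.152. Zero correlation is allowed by the plan's non-negative-correlation condition, so a ceiling of 0.1203 should hold there, and it does not. Without the stage 1 rule, the PFS criterion alone (0.137) exceeds 0.1203 whatever the correlation.

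**Step 4: progression dated to scans.** Week 18 is 126/30.4375 = 4.14 months (4.37 with +7 days). Week 27 is 189/30.4375 = 6.21 months (5.98 with −7 days). If every event is found at a scheduled scan, the rule asks whether at least 14 of 27 are progression-free at week 18. If 3.6 months is the true progression-time median, S = 0.5^(4.14/3.6) = 0.451 and P(Bin(27, 0.451) ≥ 14) = 0.302. Simulation with the visit window gives 0.299 to 0.303.

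| Rule | PFS type I error | Power at 4.8 | Power at 5.6 | Overall error, no stage 1 rule | Overall error, with stage 1 rule |
|---|---|---|---|---|---|
| As stated | 0.0744 | 50% | 77% | at most 0.1203 | not given |
| Kaplan-Meier, exact times | 0.137 | 50% | 71% | 0.173 | 0.152 |
| Kaplan-Meier, all events scan-dated | 0.302 | 70% | 85% | 0.331 | 0.28 to 0.29 |
| Kaplan-Meier, scans, 30% of events exactly dated deaths (assumed share) | 0.24 | not run | not run | 0.28 | 0.24 |

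Adding 10% dropout by 6 months (also assumed) lowers the last row to 0.23 for PFS and 0.22 overall with the stage 1 rule.

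**The case against.** The strongest reply is that nothing was miscalculated. The plan gives a planning approximation under stated assumptions, calls the study exploratory, and sets its criteria on clinical grounds. The Simon ORR design, not the PFS calculation, fixes 13 and 27. SAP 3.5 records that development had stopped, SAP 4 plans no significance test, and SAP 9 lists efficacy without summarising it. All of this stands and limits the consequence. It does not make 0.0744 the error rate of a Kaplan-Meier rule.

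Three stronger readings are tempting, and the documents do not support them.
- **That the true PFS error is 0.30.** This is an upper end. It needs 3.6 months to be the underlying progression-time median, a strict 9-week grid and no exactly dated deaths. Protocol 8.1.2 allows earlier imaging, standard-of-care scans may be used, and deaths count as PFS events on their own date. If 3.6 months were instead a scan-recorded benchmark (true median about 2.8 months by matching means), the scan-read error would be about 0.07 and the overall error about 0.11. Neither document says which is meant. The literal reading, exponential PFS with median 3.6 months, gives 0.137.
- **That power is overstated throughout.** With scan dating, PFS power is higher than stated. It is lower only at 5.6 months with exact times (71% against 77%).
- **That the joint power figures contradict the Simon design.** SAP 3.3 says "There is at least 70% power to meet at least one of the test criteria if ORR=0.25 and median PFS=4.8", and at least 79% when the median is 5.6 months. The ORR criterion alone gives 92% at ORR 0.25, which satisfies both lower bounds. They are loose, but valid.

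**Conclusion.** The point holds as a mismatch between the quoted operating characteristics and the decision rule. For the Kaplan-Meier median, the protocol's own assumptions give a PFS type I error of about 0.137 against a stated 0.0744, and power of about 71% against 77% at 5.6 months. The overall error is about 0.15 with the stage 1 rule and 0.17 without it, against a stated ceiling of 0.1203. These results need no scan assumption; the overall figures also take ORR as independent of PFS. If 3.6 months is the true progression-time median and progression is dated to 9-weekly scans, the PFS error is about 0.24 to 0.30 and the overall error about 0.24 to 0.29 with the stage 1 rule, depending on the share of exactly dated deaths (0 to 30%, assumed). Severity is moderate.

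**What to change.** In Protocol 10.2.4 and SAP 3.3, do one of the following.
- Keep the Kaplan-Meier rule and restate its operating characteristics: PFS type I error about 0.14 with exact times and up to about 0.30 with 9-weekly scans, with the matching power. Replace the 0.1203 bound. Say whether 3.6 months is a true or a scan-recorded median, and state the assumptions on deaths, ORR–PFS correlation and the stage 1 rule.
- Define the PFS criterion on the exponential-model median that 0.0744 describes, and confirm its error under the scan schedule by simulation before quoting it. With exact times, simulation of that estimator gave 0.063, and power of 48% at 4.8 and 75% at 5.6 months, so 0.0744 is itself a large-sample approximation.

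Either choice costs some rewording and a short simulation, with no added subjects or scans. The first makes the published error rate look less favourable; the second makes the decision depend on a parametric model.

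### The printed PFS error rate (0.0744) and power (77%) belong to an exponential-model median; for the Kaplan-Meier median the plan names they do not hold, nor does the overall bound of 0.1203

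*Protocol*

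**What the plan says.** Protocol 10.2.4 sets the final rule for a Phase 2 arm: "The Arm will be considered successful if 4 or more subjects respond or the median PFS is at least 4.8 months". For the PFS half it gives these operating characteristics:

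- The test "has a Type I error rate of 0.0744 when the null hypothesis is that the median" PFS is 3.6 months.
- "there is approximately 77% power to detect a median PFS of 5.6 months", and 50% power at 4.8 months.
- The planning assumptions are exponential PFS and "accrual is uniform, and total study duration is 30 months for 27 subjects enrolled over 24 months".

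It then combines PFS with the response criterion. Assuming non-negative correlation, "the overall Type I error for either test criteria being met is at most 0.1203". SAP 3.3 repeats these figures: the test "has a Type I error rate of 0.0744" under the same model ("null hypothesis is that the median PFS=3.6 months, PFS is exponentially distributed").

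The estimator appears elsewhere, in Protocol 10.2.1.2: "Kaplan-Meier methodology will be used to estimate median PFS for each cohort in Phase 1 and in each Arm in Phase 2". Neither document plans a parametric estimate of the median.

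**The concern.** An exponential-model median uses every event time. A Kaplan-Meier median from 27 subjects rests on the 14th ordered time and is less precise. A fixed threshold applied to a noisier estimate is passed more often when the true median lies below it and less often when it lies above. If the printed rates were worked out for the first estimator and the rule is applied with the second, both are too favourable.

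Meeting the PFS criterion alone is enough to call an arm successful. The plan quotes the error to four decimals and gives an upper limit for the whole rule. Anyone judging an arm against 4.8 months would take these as the chance that an inactive arm passes.

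**Working it through.** **Inputs.** Protocol 10.2.4: n = 27 per arm, accrual 24 months, total 30 months (so minimum follow-up 30 − 24 = 6 months), null median 3.6 months, threshold 4.8 months, response rate 0.05 under the null. Protocol 10.2.3: stop after 13 subjects if there is no response and median PFS is below 4.8 months.

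**1. Reproducing the printed figures.** With L = ln 2 / median, the chance of an observed event is 1 − [exp(−6L) − exp(−30L)]/(24L). Treat the log of the estimated exponential median as normal with variance 1/expected events.

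- Median 3.6: 27 × 0.9325 = 25.18 events; z = ln(4.8/3.6) × √25.18 = 1.444; upper tail 0.0744.
- Median 5.6: 27 × 0.8480 = 22.90 events; z = ln(4.8/5.6) × √22.90 = −0.738; upper tail 0.770.
- Median 4.8: z = 0; 0.50.

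All three printed values are matched.

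**2. Kaplan-Meier median, single look at 27.** Minimum follow-up (6 months) exceeds 4.8, so without dropout nobody is censored before the threshold. The Kaplan-Meier median is then at least 4.8 months exactly when at least 14 of 27 are progression-free at 4.8 months. That probability is binomial with p = 2^(−4.8/median).

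- Median 3.6: p = 0.397; P(Bin(27, 0.397) ≥ 14) = 0.137.
- Median 5.6: p = 0.552; probability 0.708.
- Median 4.8: p = 0.5; probability 0.50.

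Simulating Kaplan-Meier with the stated accrual (100,000 runs) gave 0.138, 0.707 and 0.500.

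**3. Adding the stage 1 stop.** Let r1 be the responses and s1 the subjects progression-free at 4.8 months among the first 13. The arm continues if r1 ≥ 1 or s1 ≥ 7 (each stage 1 subject assumed followed for 4.8 months before the decision). With independence, an inactive arm continues with probability 1 − 0.95^13 × (1 − 0.2217) = 0.600. Over the continuing (r1, s1), sum b(13, r1, 0.05) × b(13, s1, 0.397) × P(Bin(14, 0.397) ≥ 14 − s1), where b is the binomial probability.

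- PFS-only Type I error: 0.114. If responders are always the subjects with the longest PFS (maximal positive correlation), the same sum over the joint distribution gives 0.116. Hence about 0.115.
- PFS-only power at 5.6 months with response rate 0.20: 0.700. If the response rate stays at 0.05 it falls to 0.634, because more arms stop early.

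**4. Overall error for either criterion.** The response design (continue with at least 1 of 13, succeed with at least 4 of 27) has exact error 0.0416 with its own stop and 0.0437 without.

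| Basis | Overall Type I error |
|---|---|
| Stage 1 stop, independence | 0.151 |
| Stage 1 stop, maximal positive correlation | 0.144 |
| No stop, independence: 1 − (1 − 0.0437)(1 − 0.137) | 0.175 |
| Printed maximum | 0.1203 |

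The source of 0.1203 could not be traced. Combined with 0.0744 under independence, a response error of 0.0416 gives 0.1129 and a nominal 0.05 gives 0.1207; 0.1203 itself needs about 0.0496. It is a valid upper limit for 0.0744 with the exact response error, and fails once the Kaplan-Meier rule is used.

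**5. Sensitivity.** The documents give no dropout rate. Assuming a hazard of 1 to 3% per month, simulation gives a single-look error of about 0.147 to 0.152 and power of about 0.70 to 0.72.

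Scans are every 9 weeks (Protocol 8.1.2), so weeks 9, 18 and 27 fall at 2.07, 4.14 and 6.21 months (63, 126 and 189 days / 30.4375). If progression is dated only at on-time scans and no one dies between them, passing needs 14 of 27 without progression at week 18. P(Bin(27, 2^(−4.14/3.6)) ≥ 14) = 0.30; the same calculation at 5.6 months gives power 0.85.

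**The case against.** The strongest objections are these.

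- **The estimator is inferred.** The decision rule in 10.2.3 and 10.2.4 says only median PFS. True, but Kaplan-Meier is the only method named for that quantity. What stands is that 0.0744 is not a slip of arithmetic: it is right, as an approximation, for its own model. The fault is a mismatch between planning model and analysis estimator.
- **The single-look figure ignores the stage 1 stop.** A reader might infer from 0.137 against 0.0744 that an inactive arm passes on PFS almost twice as often as stated. With the stop the ratio is about 0.115/0.0744 = 1.5. A reader might likewise take 0.175 as the overall error, but this trial has the stop, so about 0.15 applies.
- **The replacement figures are idealised too.** This stands. They assume continuous observation and no dropout. Scan-based dating raises the error further and would put power above 77%, so the 0.71 is no safer than the printed value unless its assumptions are given.
- **No planned analysis uses these rates.** The protocol calls the study exploratory, with criteria based on clinical judgement. SAP 4 plans no significance test, SAP 9 lists efficacy without summaries, and SAP 3.5 records that development had ceased. This lowers the priority, but SAP 3.3 still prints the figures as design properties.

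**Conclusion.** The point holds. With exponential PFS, 27 subjects, at least 6 months of follow-up, no dropout and continuous observation, the Kaplan-Meier PFS criterion has single-look Type I error 0.137 (printed 0.0744) and power 0.71 at 5.6 months (printed about 77%). The 50% at 4.8 months is unchanged on that single-look basis. With the stage 1 stop, the PFS-only error is about 0.115 and power about 0.70 (the latter at a response rate of 0.20).

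The overall error is about 0.15 with the stop, so the 0.1203 maximum fails at both independence and maximal positive correlation. The two overall power statements in 10.2.4 (at least 70% and at least 79%) remain true as lower limits: with the stop and independence, the sum in step 3 extended to either criterion gives about 0.96 and 0.97.

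Two further readings are not supported. The documents give no basis for faulting a two-arm error rate, since 10.2.4 says Type I error is not controlled over both arms and prints no such figure. Nor is a final efficacy test invalidated, since the SAP plans none. This is a should-fix.

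**What to change.** In Protocol 10.2.4 and SAP 3.3, name the estimator used in the PFS decision rule, then do one of the following.

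- **Keep Kaplan-Meier.** Restate the PFS Type I error as 0.137 single-look (about 0.115 with the stage 1 stop), power at 5.6 months as about 0.71 (0.70 with the stop, at a response rate of 0.20), and the overall Type I error as about 0.15. Say that these assume continuous observation and no dropout. Simulating the full rule with the stage 1 stop and the 9-week scan schedule is preferable.
- **Use the exponential-model median** (ln 2 × total time at risk / events) as the decision statistic, to which the printed figures belong. They are normal approximations: simulating that estimator gave 0.065 and 0.75. Show how 0.1203 was obtained.

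The cost is wording and, for the preferred route, a short simulation. No subjects or data are added, but under the first option the stated error rates become less favourable.
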